10.1. Stopping Rules

Anytime, if a case of any serious adverse (drug) reaction (SAR) occurs, subject enrollment and treatment administration will be put on-hold or stopped. The study can be resumed only after the case has been discussed in a formal safety data review meeting with Sponsor's Team and the Principal Investigators.

10.2. Blinding

This is an open-label study.

11. Statistical analysis and methods

11.1. Multiplicity adjustment

N/A

11.2. Descriptive statistics

All study variables will be presented by treatment/period/sequence and overall, by using the appropriate descriptive statistics according to the variable nature, unless otherwise specified:

- Continuous variables: number of non-missing observations, mean, standard deviation, standard error of the mean, minimum, median, maximum.
- Categorical variables: number of non-missing observations and column percentages (N, %).
- PK parameters: arithmetic mean (90% CI), Standard Deviation (SD), Coefficient of Variation (CV%), geometric mean (GM) (90% CI), geometric SD, geometric CV%, minimum, median and maximum.

Results will be presented by study populations, as appropriate.

When estimating the mean or median value for the concentration at a given time point (descriptive mean or median curve), a value of 0 will be assigned to below LLOQ (BLOQ) values. The mean/median value at a time with one or more BLOQ values will be reported (in tabular or graphical fashion) unless the mean/median value is below the LLOQ of the assay, in which case the value will be assigned BLOQ.

All the baseline characteristics will be summarized through descriptive statistics overall.

11.3. Data imputation

The missing values will not be imputed because an observed-cases approach will be applied.

It will be assumed that all pharmacokinetic parameters except t_{max} follow a lognormal distribution. In particular, C_{max} , $AUC_{(0-t)}$ and $AUC_{(0-\infty)}$ will be transformed with the natural logarithm for inferential analyses (ANOVA), in order to have normally distributed data.

11.4. Patient disposition and Baseline tables

The number of enrolled subjects will be used for the patient disposition summaries, which will be summarized by sequence and overall.

The following information will be provided:

1. Number (%) of patients who are screened.
2. Number (%) of patients who are screening failures.
3. Number (%) of patients who entered the Safety population.
4. Number (%) of patients who completed the study.
5. Number (%) of patients who discontinued study treatment.
6. Number (%) of patients who entered the PK population.

Demographic baseline characteristics will be based on both PK and safety populations and will provide descriptive statistics regarding age, BMI, height, weight, ethnicity, race and gender, summarized by sequence and overall. The same table will be also provided, for the PK population only, stratified by gender and overall.

11.5. Safety analysis

11.5.1 Safety assessment

The safety assessment will be based on the following measurements / evaluations performed to monitor subjects' safety along the study at specific time points according to the study flow-chart (section 5.3):

- Physical examination and vital signs.
- Safety laboratory tests.
- 12-lead ECG.

11.5.2 Adverse Events

The safety analysis will be run on the safety population and will encompass AEs, laboratory tests, physical examination, vital signs and 12-lead ECG data. It will be carried on by using descriptive statistics.

- AEs will be coded according to the last version of the MedDRA available at the start of the study.
- TEAEs will be presented by treatment/sequence and tabulated by causal relationship, intensity, seriousness and discontinuation of treatment. TEAEs will be also summarised by primary System Organ Class (SOC) and preferred term (PT). For each PT / SOC, number of TEAEs, number and percentage of subjects with TEAE will be overall listed and stratified by

intensity (mild, moderate and severe) and by their relationship to the study drugs (related/not related).

- SAEs will be analogously analysed as TEAEs.
- ADRs will be analogously analysed as TEAEs.
- AE/SAE not considered TEAE will be included in a separate listing
- Other Safety Variables: Descriptive statistics for absolute value and change of vital signs, 12-lead ECG, physical examination, laboratory tests will be presented by time point, sequence and overall. For these variables, the changes versus baseline (i.e. last assessment prior to dosing) will be presented by sequence and overall.

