10.3.6 Safety Analysis

The safety analysis will be run on the safety population and will encompass AEs, laboratory tests, physical examination, vital signs and 12-lead ECG data. It will be carried on by using descriptive statistics.

- AEs will be coded according to the last version of the MedDRA available at the start of the study.
- TEAEs will be presented by treatment/sequence and tabulated by causal relationship, intensity, seriousness and discontinuation of treatment. TEAEs will be also summarised by primary System Organ Class (SOC) and preferred term (PT). For each PT / SOC, number of TEAEs, number and percentage of subjects with TEAE will be overall listed and stratified by intensity (mild, moderate and severe) and by their relationship to the study drugs (related/not related).
- SAEs will be analogously analysed as TEAEs.
- ADRs will be analogously analysed as TEAEs.
- AE/SAE not considered TEAE will be included in a separate listing
- Other Safety Variables: Descriptive statistics for absolute value and change (versus baseline, i.e. last assessment prior to dosing) of vital signs, 12-lead ECG, physical examination, laboratory tests will be presented by time point, sequence and overall.

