5.1. Study configuration and structure

[figure not shown]
This will be an open label, randomized, two treatment, three period, three sequence, single dose partial replicate cross-over study to assess the bioequivalence of the Nebivolol/Ramipril 5/10 mg FDC (Test) versus Nebivolol 5 mg and Ramipril 10 mg administered as extemporaneous combination (Reference).

The study population will include 54 healthy males and females (18 subjects per each randomized sequence), aged 18 to 60 years inclusive, who successfully pass the Screening procedures and will receive single doses of Test and Reference formulations according to the assigned randomized sequence A, B or C, as described in the schematic study design in the section 5.2.

Subjects will undergo a Screening (to be performed within overall 4 weeks prior to 1st study PK session), three PK sessions with one single dose administration of the Test Formulation in one out of the 3 PK sessions and one single dose of the Reference Formulation in two of the 3 PK sessions as per sequence assigned by randomization. Each PK session is separated by a minimum of a 14-day period between each IMP intake. In each PK session, blood sampling for PK plasma assessment will be taken at predefined time points up to 72 hours (h) post-dose. An End of Study Visit will be performed 10-12 days after last treatment administration, resulting in an expected individual overall clinical study duration of about 10 weeks. In case of any serious adverse (drug) reaction (SAR), subject enrollment and treatment administration will be put on-hold or stopped. The study will be resumed only after the case has been discussed and a decision on how to proceed has been taken by the Sponsor.

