- Table 1.13: Descriptive statistics of PK parameters of Nebivolol (after extemporaneous combination intake) by sequence – Analysis Population: PK population
- Table 1.14: Descriptive statistics of PK parameters of Ramipril (after FDC intake) by sequence – Analysis Population: PK population
- Table 1.15: Descriptive statistics of PK parameters of Ramipril (after extemporaneous combination intake) by sequence – Analysis Population: PK population
- Table 1.16: Descriptive statistics of PK parameters of Ramiprilat (after FDC intake) by sequence – Analysis Population: PK population
- Table 1.17: Descriptive statistics of PK parameters of Ramiprilat (after extemporaneous combination intake) by sequence – Analysis Population: PK population
- Table 1.18 Bioequivalence analysis for $AUC_{(0-t)}$, C_{max} and $AUC_{(0-\infty)}$ of Nebivolol including group effect (sensitivity analysis) – Analysis Population: PK population
- Table 1.19: Bioequivalence analysis for $AUC_{(0-t)}$, C_{max} and $AUC_{(0-\infty)}$ of Ramipril including group effect (sensitivity analysis) – Analysis Population: PK population

Safety analysis (safety population)

- Table 2.1.1.1: Overview AEs by Sequence – Analysis Population: Safety
- Table 2.1.1.1: Overview AEs by Treatment – Analysis Population: Safety
- Table 2.1.1: Overview TEAEs by Sequence – Analysis Population: Safety
- Table 2.1.2: Overview ADRs by Sequence – Analysis Population: Safety
- Table 2.2.1: Overview TEAEs by Treatment – Analysis Population: Safety
- Table 2.2.2: Overview ADRs by Treatment – Analysis Population: Safety
- Table 2.3.1: TEAEs by MedRa, SOC and PT by Sequence – Analysis Population: Safety
- Table 2.3.2: ADRs by MedRa, SOC and PT by Sequence – Analysis Population: Safety
- Table 2.3.3: TEAEs by MedRa, SOC and PT by Intensity and Sequence - Analysis Population: Safety
- Table 2.3.4: TEAEs by MedRa, SOC and PT by Causality and Sequence – Analysis Population: Safety
- Table 2.3.5: ADRs by MedRa, SOC and PT by Intensity and Sequence – Analysis Population: Safety
- Table 2.3.6: ADRs by MedRa, SOC and PT by Causality and Sequence – Analysis Population: Safety
- Table 2.4.1: TEAEs by MedRa, SOC and PT by Treatment – Analysis Population: Safety
- Table 2.4.2: ADRs by MedRa, SOC and PT by Treatment – Analysis Population: Safety

-
- Table 2.4.3: TEAEs by MedRa, SOC and PT by Intensity and Treatment – Analysis Population: Safety

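### By-treatment adverse event tables are not adjusted for two Reference doses against one Test dose per subject, so Reference tends to look worse by design

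*SAP*

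**What the plan says.** SAP 5.1 has every subject take Test in a single session, whereas for Reference it plans "one single dose of the Reference Formulation in two of the 3 PK sessions". The sequence tables in Protocol 9.3.2 and SAP 9 agree: each of the three sequences holds one Test and two Reference sessions.

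For adverse events, Protocol 10.3.6 says "TEAEs will be presented by treatment/sequence", and SAP 11.5.2 repeats this. The counting units named in SAP 11.5.2 are "number of TEAEs, number and percentage of subjects with TEAE", and ADRs and SAEs are to be handled in the same way. SAP 6.4 supplies a matching display format, an event count beside a count with its percentage.

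The table index in SAP 13.2.1 lists these by-treatment outputs:

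- the by-treatment AE overview (numbered 2.1.1.1, a number it shares with the by-sequence overview);
- "Table 2.2.1: Overview TEAEs by Treatment" and its ADR counterpart, 2.2.2;
- Tables 2.4.1 to 2.4.6, beginning with "TEAEs by MedRa, SOC and PT by Treatment".

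Tables 2.3.1 to 2.3.6 are by sequence. No adverse event table is titled by period or per administration, and no text defines the denominator of the Test and Reference columns.

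**The concern.** In a two-period crossover every subject contributes one exposure to each treatment, so the percentage of subjects with an event can be read straight across the columns. Here it cannot. A subject has two chances to enter the Reference column and one chance to enter the Test column. If the tables count subjects or raw events, Reference shows more of both even when the two formulations are equally well tolerated.

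The protocol synopsis gives as its secondary objective the safety and tolerability of single oral doses in the two forms, and the incidence of TEAEs is the stated safety endpoint. The by-treatment tables are the only treatment-level summary of that endpoint. A reader of the study report would set the two columns side by side and could take an exposure artefact for a difference between products.

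**Working it through.** **Inputs.** 54 subjects randomised (Protocol 10.1, SAP 8); one Test and two Reference doses per subject (SAP 5.1). The 54 is consistent with the plan's own allowance: 42 / (1 − 0.22) = 53.8, rounded up to 54. The documents state no adverse event rate, so the per-dose probability p of at least one event is an assumption, taken as equal for Test and Reference.

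**Planned administrations.** Test 54 × 1 = 54; Reference 54 × 2 = 108.

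**Event counts.** With the same expected number of events per dose, the expected totals stand at 108 : 54 = 2 : 1. Correlation between a subject's periods does not change this.

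**Percentage of subjects with an event, independent doses.** Test: p. Reference: 1 − (1 − p)². Ratio: [1 − (1 − p)²] / p = 2 − p.

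| p per dose | Test | Reference | Ratio | Expected subjects of 54, Test vs Reference |
|---|---|---|---|---|
| 1% | 1.0% | 2.0% | 1.99 | 0.5 vs 1.1 |
| 5% | 5.0% | 9.75% | 1.95 | 2.7 vs 5.3 |
| 10% | 10% | 19% | 1.90 | 5.4 vs 10.3 |
| 20% | 20% | 36% | 1.80 | 10.8 vs 19.4 |
| 30% | 30% | 51% | 1.70 | 16.2 vs 27.5 |
| 50% | 50% | 75% | 1.50 | 27.0 vs 40.5 |

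**Correlated doses.** With correlation ρ between the two Reference periods, the probability of an event in both is p² + ρp(1 − p), so the ratio becomes 2 − p − ρ(1 − p). At p = 10%:

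- ρ = 0.1: 1.90 − 0.09 = 1.81
- ρ = 0.3: 1.90 − 0.27 = 1.63
- ρ = 0.5: 1.90 − 0.45 = 1.45
- ρ = 1: 1.90 − 0.90 = 1.00

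**Early dropout.** Suppose 12 subjects leave, four per sequence, and percentages use subjects exposed to the treatment, with p = 10% and independent doses.

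- Leaving after session 1: 50 subjects have any Reference dose, 42 of them two doses and 8 one. (42 × 0.19 + 8 × 0.10) / 50 = 0.1756, ratio 1.76.
- Leaving after session 2: 54 have any Reference dose, 46 two and 8 one. (46 × 0.19 + 8 × 0.10) / 54 = 0.1767, ratio 1.77.

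**Per-administration basis.** Administrations with at least one event over administrations given has expectation p for both treatments, so the ratio is 1.00 whatever p or ρ is.

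**The case against.** Four points can be made for the plan.

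- **The denominator is inferred.** The sentence naming subject counts and percentages goes on to describe an overall listing with strata for intensity and relationship. The by-treatment tables exist only as titles, with no shells. This stands in part: the plan does not state a Test or Reference denominator. But the subject and the event are the only counting units named in SAP 11.5.2, SAP 6.4 gives the matching format, and the safety population is defined by subject. No per-dose unit appears anywhere.
- **SAP 11.2 has a general rule that includes period.** It yields where something else is specified, and every adverse event table title specifies treatment or sequence. The PK parameter tables 1.3 to 1.5, by contrast, are titled by treatment and period.
- **The listings allow reconstruction.** L14 and L15 carry period and treatment, L15 adds the first exposure time in each session, and L16 lists the administrations. This is true and shows that the remedy needs no new data. It does not correct the summary tables.
- **Safety is descriptive only.** No test, margin or decision depends on these tables, and the safety objective in the synopsis is not repeated in Protocol 7 or SAP 4.1. This stands and limits the weight of the point.

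A reader might go further and infer that Reference will show nearly double the incidence. That holds only for infrequent events with nearly independent doses. The same volunteers take the same products twice, so some positive correlation is plausible, and the ratio then falls well below 2.

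**Conclusion.** The point holds for the by-treatment AE overview and Tables 2.2.1, 2.2.2 and 2.4.1 to 2.4.6. As described, they carry no adjustment for the 2:1 exposure. Under equal per-dose risk, expected event counts are 2:1. The ratio of subject percentages is 2 − p for independent doses, is smaller with positive correlation, and equals 1 only when the two Reference periods are perfectly correlated. The sizes rest on assumed values of p and ρ; the direction does not depend on p.

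The consequence is limited to how the descriptive safety summary reads. The bioequivalence conclusion does not use these tables. The by-sequence tables, 2.3.1 to 2.3.6 among them, are undistorted because every sequence has the same mix of one Test and two Reference doses. A reader might also infer that the plan sets up a formal safety comparison tilted towards the fixed-dose tablet. The documents do not support that: they plan no between-treatment safety test, they state the 2:1 dosing openly, and they leave the column denominators undefined rather than choosing a biased one.

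**What to change.** In each by-treatment adverse event table:

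- show in the column header the number of administrations actually given. The planned figures are 54 Test and 108 Reference; dropout, and the replacement of subjects provided for in SAP 8, may change them;
- report administrations with at least one event over administrations given, and events per administration;
- state that each TEAE is assigned to the most recent dose, using the session exposure times already held in L15. A rule is needed because the TEAE definition in SAP 7.2.2 refers only to the first study drug intake.

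Percentages of subjects may stay as a supplement if their denominators are stated. The by-sequence tables need no change on this account. The cost is revised table shells and programming, with no new data.

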9.4.1.3 Pharmacokinetic Study Sessions

Subjects will be resident at the study site from the evening of the day prior to each PK study session until the 72-h post dosing, after PK sampling and study procedures have been completed.

Each study session should be separated by a minimum of 14-day wash-out period between each IMP intake.

Subjects must abstain from extraneous exercise during residence at the study site.

Study procedures to be applied to the PK study sessions are described below.

Pre-dosing procedures will be performed as follows:

NOTE: pre-dosing procedures can be performed on Day - 1, i.e. the day before dosing, the only exception being the 'Baseline' procedures listed below)

- Recording of any Clinical Event, not associated to any drug intake (Clinical Event; § 9.5.2.3 NOTE) and/or of any Adverse Event (§ 9.5.2.3), associated to any drug intake that occurs for the first time or worsens after the signature of the Informed Consent and prior to IMP administration, if any, and/or any medication change since the screening visit/previous study session, if any.
- Check of adherence to the study restrictions.
- Physical examination.
- Urine collection for:
 - Pregnancy test (β -HCG in urine) in female of childbearing potential.
 - Drugs of abuse screening test for cocaine and metabolites (COC 300), Amphetamine (AMP 500), Methamphetamine (MET 500), Marijuana (including Cannabinoids THC) (THC 50), Opiates (including Heroin Morphine and metabolites) (MOP 300), Methylenedioxymethamphetamine Ecstasy (MDMA 500), Methadone (MTD 300).
 - Cotinine test.
- Alcohol salivary test.
- Re-check of inclusion/exclusion criteria.
- Randomization (applicable to 1st PK session only).
- Baseline recording (T+0'), within 1 hour from dosing of vital signs including Frontal Body Temperature, supine SBP and DBP, PR, RR and 12-lead ECG, to be measured after at least 10-minute rest.
- Baseline blood sample (T+0') of 8 mL for PK plasma assay within 30 minutes from dosing.

Dosing will start after baseline (prior to dosing) procedures are completed, with one of two oral treatments to be administered as per randomization sequence:

- NEB/RAM 5/10 mg FDC;
- NEB 5 mg + RAM 10 mg EC;

All treatments shall be orally taken in the morning, at $8:00 \pm 1$ h, in fasting condition with 240 mL of still water.

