7.2.2. Key definitions

Baseline values

The baseline value of an assessment is defined as the last value measured before any intake of the study drugs.

Adverse Events (AEs)

Any untoward medical occurrence in a subject or clinical trial subject administered a medicinal product and which does not necessarily have a causal relationship with this treatment.

An AE can therefore be any unfavourable and unintended sign (including an abnormal laboratory finding), symptom, or disease temporally associated with the use of a medicinal product, whether considered related to the medicinal product.

Treatment-Emergent Adverse Events (TEAEs)

A Treatment-Emergent Adverse Event (TEAE) stands for an AE that occurs for the first time or that worsens in terms of seriousness or severity after the first study drug intake.

Drug Relationship

The relationship between an AE and study drugs will be judged according to the following categories:

Certain: The AE occurs in a plausible time relation to the administration of the drug and cannot be explained by a concurrent disease or other drugs or chemicals. The response to withdrawal of the drug (dechallenge) should be clinically plausible. The event must be definitive pharmacologically or phenomenologically, using a satisfactory rechallenge procedure if necessary.

Probable: The AE occurs in a reasonable time relation to the administration of the drug, it is unlikely to be attributed to a concurrent disease or other drugs or chemicals and it follows a clinically reasonable response on withdrawal (dechallenge). Rechallenge information (AE reappearance after drug reintroduction) is not required to fulfil this definition.

Possible: The AE occurs with a reasonable time relation to the administration of the drug, but it could also be explained by a concurrent disease or other drugs or chemicals. Information on drug withdrawal (dechallenge) may be lacking or unclear.

Unassessable: The relationship cannot be judged because the information is insufficient or contradictory and cannot be supplemented or verified.

Unlikely: A causal relationship cannot be definitively ruled out, but other drugs, chemicals, or underlying disease provide plausible explanations and/or the temporal relation to the administration of the drug makes a causal relation improbable.

Not Related: Any of the following are present:

- existence of a clear alternative explanation, and/or;
- unreasonable temporal relationship between drug and event, and/or;

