11.5.3. Physical Examination and Vital Signs

A summary table of Vital Signs parameters described in protocol section 9.4.3.3 will be provided in the TLFs. Descriptive statistics for absolute value and change versus baseline for vital signs (i.e., last assessment prior to dosing) will be presented by time point, treatment and overall.

Investigator judgement (clinically significant/not clinically significant) for vital signs will also be presented by sequence and time point.

Height (in cm), weight (in kg) and BMI calculation (is calculation will be performed in the eCRF) will be analyzed in the baseline table as discussed in section 11.2.

11.5.4. 12-ECG

The 12-lead ECGs will be performed after at least 10-minute rest in supine position, at the time points reported in the study flow chart (section 5.3). The Investigator or a designee will evaluate whether they are normal or abnormal and, if abnormal, whether they are clinically significant. Any occurrence of abnormalities in the cardiac conduction, depolarisation, repolarisation, arrhythmic events and other abnormalities will be evaluated.

The ECG report should be identified with subject details as well as the date and time of recording.

The dated and signed printed version of the ECG will be regarded as source data.

ECGs may be repeated for quality reasons and the results of the repeated ECG will be analysed. Unscheduled ECGs may be collected by the Investigator for safety reasons.

Clinically relevant abnormal findings detected after the signature of the ICF will be reported as AEs in the eCRF.

12-lead ECG parameters will be analyzed on the safety population by means of descriptive tables, similarly to Vital Signs, that will be provided in the TLF. ECG overall investigator judgement will be reported by descriptive statistics by sequence and time point.

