 - Table 2.4.4: TEAEs by MedRa, SOC and PT by Causality and Treatment – Analysis Population: Safety
 - Table 2.4.5: ADRs by MedRa, SOC and PT by Intensity and Treatment – Analysis Population: Safety
 - Table 2.4.6: ADRs by MedRa, SOC and PT by Causality and Treatment – Analysis Population: Safety
 - Table 2.5: Haematology by sequence and Visit and their change versus baseline – Analysis Population: Safety
 - Table 2.6: Biochemistry by sequence and Visit and their change versus baseline – Analysis Population: Safety
 - Table 2.7: Urinalysis by sequence and Visit and their change versus baseline – Analysis Population: Safety
 - Table 2.8: Vital signs by sequence and Time Point and their change versus baseline – Analysis Population: Safety
 - Table 2.9: ECG by sequence and Time Point and their change versus baseline – Analysis Population: Safety
 - Table 2.10: Haematology Investigator Judgment by Sequence and visit – Analysis Population: Safety
 - Table 2.11: Biochemistry Investigator Judgment by Sequence and visit – Analysis Population: Safety
 - Table 2.12: Urinalysis Investigator Judgment by Sequence and visit – Analysis Population: Safety
 - Table 2.13: ECG Investigator Judgment by Sequence and time point – Analysis Population: Safety
 - Table 2.14: Vital signs Investigator Judgment by Sequence and time point – Analysis Population: Safety
 - Table 2.15: Serology by sequence (HIV-1, HIV-2, hepatitis B, hepatitis C and SARS-CoV-2) – Analysis Population: Safety
 - Table 2.16: Toxicology: Alcohol breath test, drugs abuse and Cotinine Test by sequence – Analysis Population: Safety

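### The SAP promises vital signs and ECG by treatment but plans tables only by sequence, and it defines their baseline in two different ways

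*SAP*

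**What the plan says.** **Grouping.** For vital signs, ECG, physical examination and laboratory tests together, SAP 11.5.2 states that "12-lead ECG, physical examination, laboratory tests will be presented by time point, sequence and overall". It adds that "the changes versus baseline (i.e. last assessment prior to dosing) will be presented by sequence and overall". SAP 11.5.6 repeats the sequence layout, which comes from protocol 10.3.6. SAP 11.5.3, the section specific to vital signs, says that absolute values and changes for "vital signs (i.e., last assessment prior to dosing) will be presented by time point, treatment and overall". SAP 11.5.4 then says that "12-lead ECG parameters will be analyzed on the safety population by means of descriptive tables, similarly to Vital Signs". The table index in SAP 13.2.1 has "Table 2.8: Vital signs by sequence and Time Point and their change versus baseline" and, in the same layout, Table 2.9 for ECG. It has no by-treatment table for either.

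**Baseline.** SAP 7.2.2 states: "The baseline value of an assessment is defined as the last value measured before any intake of the study drugs". SAP 11.5.2, 11.5.3 and 11.5.6 instead gloss baseline as the last assessment before dosing. Protocol 9.4.1.3, which lists the procedures for the PK sessions, has a baseline recording at T+0, "within 1 hour from dosing of vital signs including Frontal Body Temperature, supine SBP and DBP, PR, RR and 12-lead ECG". The flow charts apply the T+0 column to all three sessions.

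**Purpose.** The secondary objective in the protocol synopsis is safety and tolerability of the combination given as FDC and as EC. SAP 5.4.4 lists changes from baseline in vital signs and ECG among the safety endpoints.

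**The concern.** In a crossover, sequence is the order in which a subject receives the treatments, not the treatment received. A table split by sequence answers a tolerability question about two formulations only if the reader can also see which session each number comes from. The one section that promises a treatment split has no matching table, so a programmer working from the index would never produce it.

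The two baseline definitions make this worse. Two programmers following the same SAP could report different changes for the same subject in sessions 2 and 3.

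Both drugs are antihypertensives. Protocol 6.2 relies on monitoring of blood pressure, pulse and ECG as part of its risk mitigation. These are therefore data for which a plain FDC and EC summary is worth having.

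**Working it through.** The documents give no figure on this point. The check sets the passages side by side and then works through the design.

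**Step 1: text against planned output.**

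| Item | SAP text | Planned table | Agree? |
|---|---|---|---|
| Vital-sign values and changes | 11.5.3: treatment; 11.5.2 and 11.5.6: sequence | 2.8: sequence | No |
| ECG values and changes | 11.5.4: as vital signs; 11.5.2 and 11.5.6: sequence | 2.9: sequence | No |
| ECG investigator judgement | 11.5.4: sequence | 2.13: sequence | Yes |
| Vital-sign investigator judgement | 11.5.3: sequence | 2.14: sequence | Yes |
| TEAEs and ADRs | 11.5.2 (TEAEs, with ADRs handled in the same way): treatment/sequence | 2.1.x to 2.4.x: both | Yes |

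**Step 2: formulation content of a sequence.** Protocol Table 1 gives A = FDC, EC, EC; B = EC, EC, FDC; C = EC, FDC, EC. The FDC share is 1/3 in every sequence. Because the share does not vary between sequences, three sequence means pooled over complete sessions contain no information on FDC minus EC.

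**Step 3: illustration.** The values here are assumptions for demonstration, not figures from the documents: a change of −3 after EC, a further −5 after FDC, and session drift of 0, −1 and −2.5 from the first-dose baseline. Expected changes by session are:

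| Sequence | Pre-study baseline (sessions 1, 2, 3) | Mean | Same-session baseline (sessions 1, 2, 3) | Mean |
|---|---|---|---|---|
| A | −8, −4, −5.5 | −5.83 | −8, −3, −3 | −4.67 |
| B | −3, −4, −10.5 | −5.83 | −3, −3, −8 | −4.67 |
| C | −3, −9, −5.5 | −5.83 | −3, −8, −3 | −4.67 |

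Under either baseline the three pooled sequence means are identical, despite a built-in formulation difference of −5.

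**Step 4: the same cells averaged by formulation.**
- Pre-study baseline: FDC = (−8 − 10.5 − 9)/3 = −9.17; EC = (−4 − 5.5 − 3 − 4 − 3 − 5.5)/6 = −4.17; difference −5.0.
- Same-session baseline: FDC = −8; EC = −3; difference −5.0.

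The contrast is recovered under both baselines. FDC occurs once in each session, so drift balances between formulations in complete data. What differs is the reported change: in sequence B the FDC change is −10.5 under one definition and −8 under the other.

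**Step 5: age of the 7.2.2 baseline.** Doses are at least 14 days apart, so the pre-first-dose value is at least 14 days old at session 2 and at least 2 × 14 = 28 days old at session 3.

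**Step 6: if sessions are shown separately.** There are then nine sequence-by-session cells, each with a known formulation. The FDC data lie in three cells of about 18 subjects (54/3), and no planned table combines them.

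**The case against.** The strongest reply is that the documents never say sessions will be pooled. Time points sit within PK sessions, and the SAP 11.2 default is treatment/period/sequence. If Tables 2.8 and 2.9 are split by session, a reader can identify the formulation in every cell. Listings L6 and L7 carry period, and L16 links period to treatment. This stands, so a reader who infers that the planned tables cannot show any difference goes too far. It does not supply the missing table, however. Tables 1.3 to 1.5 name period when it is meant, whereas 2.8 and 2.9 do not, and the 11.5.3 commitment still has no output.

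A reader might also infer that the formulation signal between sequences is exactly zero. That requires complete data. The safety population includes anyone dosed once, so a sequence A subject who leaves after session 1 contributes only FDC data, and a sequence B subject who does so contributes only EC data.

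A third tempting reading is that the baseline is settled as pre-study and defeats the comparison. Only 7.2.2 says pre-study; the safety sections can be read as session-specific. Step 4 shows that neither choice removes the contrast.

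Nor do Tables 2.13 and 2.14 contradict their text, because investigator judgement is specified by sequence in both places. By-sequence layout also suits laboratory tests, which the flow chart schedules only at screening and end of study.

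Finally, the summaries are descriptive, the protocol's own safety endpoint is TEAEs, and clinically significant vital-sign or ECG findings are reported as AEs and so can reach the by-treatment AE tables. This limits the consequence but does not resolve the conflict.

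**Conclusion.** The point holds as two inconsistencies with a practical consequence.

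1. The SAP text for vital signs, and for ECG by reference, promises a treatment split that the other safety sections and Tables 2.8 and 2.9 do not deliver. As indexed, no table directly summarises these data by formulation. If the tables pool sessions, they carry essentially no FDC–EC contrast among subjects who complete all three sessions.
2. Baseline has two definitions that give different change scores in sessions 2 and 3, one of them using a value at least 14 or 28 days old.

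The first conclusion rests on the table titles as listed and on the Table 1 sequences. The numerical example rests on assumed effects and shows structure only. Nothing here affects sample size, alpha or the bioequivalence conclusion. It should be corrected because the planned output would otherwise not directly address the secondary objective for vital signs and ECG.

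**What to change.** - Present vital-sign and ECG values and changes (Tables 2.8 and 2.9) by formulation and time point. Keep a by-sequence version as an option.
- Define baseline for vital signs and ECG as the T+0 pre-dose value of the same session.
- Keep the single pre-first-dose baseline and the by-sequence layout for laboratory tests.
- Align SAP 7.2.2, 11.5.2, 11.5.3, 11.5.4 and 11.5.6 with these choices.
- Leave Tables 2.13 and 2.14 as they are; a by-formulation version is optional.

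The cost is SAP wording and table shells. Every assessment needed is already scheduled and recorded in each session.
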